## **5. CONDUCT OF THE STUDY**

### **5.1. Regulatory and ethical considerations, including the informed consent process**

The study will be conducted in accordance with all applicable regulatory requirements.

The study will be conducted in accordance with the ICH Guideline for GCP, all applicable subject privacy requirements and the guiding principles of the Declaration of Helsinki.

The study has been designed and will be conducted in accordance with the ICH Harmonised Tripartite Guideline for clinical investigation of medicinal products in the paediatric population (ICH E11) and all other applicable ethical guidelines.

GSK will obtain favourable opinion/approval to conduct the study from the appropriate regulatory agency, in accordance with applicable regulatory requirements, prior to a site initiating the study in that country.

Conduct of the study includes, but is not limited to, the following:

- Institutional Review Board (IRB)/Independent Ethics Committee (IEC) review and favourable opinion/approval of study protocol and any subsequent amendments.
- Subject informed consent
- Investigator reporting requirements as stated in the protocol.

GSK will provide full details of the above procedures to the investigator, either verbally, in writing, or both.

Freely given and written informed consent must be obtained from each subject prior to participation in the study.

GSK Biologicals will prepare a model Informed Consent Form (ICF) which will embody the ICH GCP and GSK Biologicals required elements. While it is strongly recommended that this model ICF is to be followed as closely as possible, the informed consent requirements given in this document are not intended to pre-empt any local regulations which require additional information to be disclosed for informed consent to be legally effective. Clinical judgement, local regulations and requirements should guide the final structure and content of the local version of the ICF.

The investigator has the final responsibility for the final presentation of the ICF, respecting the mandatory requirements of local regulations. The ICF generated by the investigator with the assistance of the sponsor's representative must be acceptable to GSK Biologicals and be approved (along with the protocol, and any other necessary documentation) by the IEC.

## **5.2. Subject identification and randomisation**

A total of 200 subjects who participated in study TBEV POLYGELINE FREE (V48)-023 EXT 021 (V48P7E2), who received in a parent V48P7 study one of the following schedules: R, C and AC and a booster vaccination in study V48P7E1 or before study V48P7E1 (only R-schedule) and agreed to participate in this study are to be enrolled.

*The subjects will have new identification numbers which will be pre-assigned with a link established to the subject identification numbers used in the previous V48P7, V48P7E1 and V48P7E2 studies.* There is no randomization in the study as only the number of subjects who will have a NT antibody titre of below 10 will receive vaccination. *However allocation of the study treatment and management of study vaccines will be done through Source DataBase for Internet Randomization (SBIR).* (Amended 23 February 2018)

For details on the sub-cohorts refer to Section [4.1](#).

### **5.2.1. Treatment allocation to the subject (who may receive vaccination in the study)**

The treatment numbers will be allocated by product.

After obtaining the signed and dated ICF from the subject and having checked the eligibility of the subject, the site staff in charge of the vaccine administration will *access SBIR* at Visit 23.1/ Visit 24.1/ Visit 25.1/ Visit 26.1/ Visit 27.1. *Upon providing the subject identification number, the randomisation system will provide the treatment number to be used for the dose.* (Amended 23 February 2018)

The number of the administered treatment must be recorded in the eCRF on the Vaccine Administration screen.

*When SBIR is not available, please refer to the SBIR user guide or the Study Procedures Manual for specific instructions.* (Amended 23 February 2018)

## **5.3. Method of blinding**

The study is open-label.

The laboratory in charge of the laboratory testing will be blinded to the treatment, subject and visit number, and codes will be used to link the subject, visit and study (without any link to the treatment attributed to the subject) to each sample.

## **5.4. General study aspects**

Supplementary study conduct information not mandated to be present in this protocol is provided in the accompanying SPM. The SPM provides the investigator and the site personnel with administrative and detailed technical information that does not impact the safety of the subjects.

## 5.5. Outline of study procedures

**Table 4 List of study procedures on scheduled visits**

Epoch	Epoch 001				
Type of contact	Visit 23	Visit 24	Visit 25	Visit 26	Visit 27
Timepoint (s)	Year 11 (132 months)	Year 12 (144 months)	Year 13 (156 months)	Year 14 (168 months)	Year 15 (180 months)
Sampling timepoint(s)	LTFU	LTFU	LTFU	LTFU	LTFU
Informed consent	•				
Check inclusion / exclusion criteria	•				
Collect demography data	•				
Medical history	•	•	•	•	•
Physical examination	•	•	•	•	•
Review of subject's continued eligibility	•	•	•	•	•
Measure/record height	•				
Measure/record weight	•	•	•	•	•
Laboratory Assays					
Blood sampling for antibody determination (~10 ml)	•	•	•	•	•
Safety assessments					
Record any concomitant medications/vaccinations	•	•	•	•	•
Record any intercurrent medical conditions		•	•	•	•
Recording of SAEs and pregnancies #		•	•	•	•
Recording of SAEs related to study participation, or to a concurrent GSK medication/vaccine	•	•	•	•	•
Study Conclusion					•

Note: Visits numbers are consecutive numbers from previous studies, timepoints are indicated starting after enrolment in study V48P7E1. Results of the immunogenicity testing will be checked yearly in order to establish if antibody titre is below 10; if below this value subject will receive their second booster dose in this study, [Table 5](#).

LV: Last Visit. LTFU: Long-term follow-up.

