## 2. OBJECTIVES

### 2.1. Primary objective

- To evaluate the persistence of antibody response to a booster dose of *Encepur Adults* vaccine starting  $\geq 11$  years after the first booster administration and to continue following subjects up to 15 years after first booster administration.

Refer to Section 10.1 for the definition of the primary endpoints.

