**Figure 2 Study design of study V48P7E1 and TBEV Polygeline-free-023 Ext:021 (V48P7E2)**

[figure not shown]

**TBE\_R\_B** = R-schedule in V48P7 and Booster before enrollment in V48P7E1; **TBE\_R** = R-schedule in V48P7 and Booster in V48P7E1; **TBE\_C** = C-schedule in V48P7 and Booster in V48P7E1; **TBE\_AC** = AC-schedule in V48P7 and Booster in V48P7E1; **C** = Conventional schedule in study V48P7; **R** = Rapid schedule study V48P7; **AC** = Accelerated Conventional schedule study V48P7; **Enrol** = Enrolment; **LV** = Last Visit; **V** = Visit; **D** = Day; **Y** = Year; **BVAC** = Booster Vaccination; **BS** = Blood Sample

\*Booster vaccination 3 years after primary vaccination in V48P7, except TBE R-B (vaccination before enrolment in V48P7E1 and BS only on Day 0)

\*\*Study group MC was not followed, it is not a registered schedule; \*\*\*last V48P7E1 visit is screening visit

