**Table 1 Study groups and epochs foreseen in the study**

Study groups	Number of subjects*	Age	Epochs
			Epoch 001
C	51	25 years and above	x
R	46	25 years and above	x
AC	103	25 years and above	x

\* Approximate number of subjects

C: Conventional schedule: Primary vaccination of 66 subjects in study V48P7 on Days 0, 28 (+10) and 300 (+21), booster vaccination of 55 subjects in study V48P7E1, no vaccination in study TBEV POLYGELINE FREE (V48)-023 EXT 021 (V48P7E2).

R: Accelerated (or "rapid") schedule: Primary vaccination of 66 subjects in study V48P7 on Days 0, 7 (+3) and 21 (+7), booster vaccination of 9 subjects in study V48P7E1 (40 subjects received their booster vaccination before enrolment in study V48P7E1), no vaccination in study TBEV POLYGELINE FREE (V48)-023 EXT 021 (V48P7E2).

AC: Accelerated conventional schedule: Primary vaccination of 133 subjects in study V48P7 on Days 0, 14 (+3) and 300 (+21), booster vaccination of 109 subjects in study V48P7E1, no vaccination in study TBEV POLYGELINE FREE (V48)-023 EXT 021 (V48P7E2).

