# Will only be collected from subjects who received a second booster vaccination in this study, all SAEs will be collected for 1 month after vaccination.

LV: Last Visit. LTFU: Long-term follow-up.

Whenever possible the investigator should arrange study visits within the interval provided in [Table 6](#). Of note, Visit 23 is the baseline visit for this study and it will need to be considered as the driver for the calculation of the interval for all subsequent visits as highlighted in the grey shaded rows of [Table 6](#).

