### 10.2. Secondary Endpoint(s)

The immunogenicity endpoints for subjects who received a second booster vaccination will be based on the TBE NT antibody levels in serum at 21 days after the booster vaccination as measured by GSK Biologicals' NT.

Measures of immunogenicity are:

- Percentages of subjects with detectable TBE Neutralizing Antibody Titres  $\geq 2$  and  $\geq 10$  as measured by GSK Biologicals' NT, overall and by study group.
- Geometric Mean Antibody Titres and Geometric Mean Ratios (GMRs) blood draw after/before booster as measured by GSK Biologicals' NT, overall and by study group.
- To complement the analysis of persistence, a thorough description of NT waning from year 1 after the first booster dose up to 15 years will be presented for the set of subjects completing the entire 15-year follow-up with no protocol deviations, including those receiving a second booster dose; for those ones, a constant value of NT = 1 from the post booster visit will be used in the analysis.

Endpoints will be summarized according to the primary immunization schedule received in the parent study (V48P7).

The safety endpoint for subjects who will need a second booster vaccination will be based on SAEs collection after the second booster dose. In vaccinated subjects all SAEs will be collected for 1 month after vaccination. Depending on the timing of the booster dose this will be in the period year 11.5 (Visit 23.1), 12.5 (Visit 24.1), 13.5 (Visit 25.1), or 14.5 (Visit 26.1) or from year 15.5 (Visit 27.1) until 21 days after year 15.5 (Visit 27.2). Post-study SAEs will be collected until study conclusion (Refer Section 8.3.2 for details on post-study SAEs)

Measures of safety are:

- Incidence of serious adverse events.

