### **10.7.2. Statistical Methods for Immunogenicity Variables**

Long-term immunogenicity (persistence).

- Percentages of subjects with neutralizing antibody titres  $\geq 2$  and  $\geq 10$  as measured by NT assay will be tabulated by vaccine schedule (as assigned from the parent study) together with the associated two-sided 95% Clopper-Pearson confidence intervals (CIs). The vaccine group difference in the percentage of subjects with neutralizing antibody titres  $\geq 2$  and  $\geq 10$  will be calculated using a binomial distribution. The associated confidence interval for these differences will be constructed using the Miettinen-Nurminen method.
- GMTs with the associated 95% CIs will be computed for each vaccine schedule (as assigned from the parent study), by taking the exponential of the corresponding log10-transformed (least squares) means and 95% confidence intervals, from an ANOVA model with group as fixed factor. Vaccine schedule differences along with 95% CIs will also be computed.

Subjects with antibody levels below 10 at a given visit (and that will therefore receive a booster dose) will be kept in the analysis of persistence also for the subsequent years with a value imputed to half of the detection limit, i.e. 1.

Analyses will be conducted on the PPS-1 (and repeated on the FAS-1, if appropriate).

Immune response to booster dose (boostability):

- Percentages of subjects with neutralizing antibody titres  $\geq 2$  and  $\geq 10$  at 21 days after administration of the booster dose, as measured by NT will be tabulated by vaccine schedule (as assigned from the parent study) together with the associated two-sided 95% Clopper-Pearson CIs.

- GMTs with the associated 95% CIs at 21 days after administration of the booster dose, will be computed for each vaccine schedule (as assigned from the parent study), by taking the exponential of the corresponding log10-transformed (least squares) means and 95% confidence intervals, from an ANOVA model with group as fixed factor.
- GMRs with the associated 95% CIs after/before booster as measured by GSK Biologicals' NT calculated for each of the different schedule groups.

Computationally, the antibody value as recorded 6 months prior to the booster visit (i.e. at the previous scheduled clinic visit) will be considered as baseline.

All analyses will be repeated for each age subgroup.

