5.3. Important protocol deviation not leading to elimination from per-protocol analysis set

Not applicable.

6. STATISTICAL ANALYSES**6.1. Demography****6.1.1. Analysis of demographics/baseline characteristics planned in the protocol**

Descriptive statistics (mean, standard deviation, median, minimum and maximum) for age, height and weight at enrolment will be calculated overall and by vaccine schedule.

Distributions of subjects by sex and ethnic origin will be summarized overall and by vaccine schedule as per parent study assignment.

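### Year 11 to 15 is counted from V48P7E1 enrolment, but the objective counts from the first booster; about four-fifths of the R group were boosted before that enrolment

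*Protocol*

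**What the plan says.** Two time origins are in use.

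- **Visit labels.** The notes under Tables 4 and 5 (Protocol 5.5) read: "timepoints are indicated starting after enrolment in study V48P7E1". Visits 23 to 27 are therefore Years 11 to 15 after that enrolment.
- **Objective and waning description.** The primary objective (Protocol 2.1, repeated in SAP 3.1) starts at 11 or more "years after the first booster administration and to continue following subjects up to 15 years after first booster administration". The secondary endpoints (Protocol 10.2, SAP 4.2) promise "a thorough description of NT waning from year 1 after the first booster dose up to 15 years".

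The first booster was given in V48P7E1 to C, to AC and to 9 R subjects. For the rest of R, the footnote to Table 1 (Protocol 3) states: "40 subjects received their booster vaccination before enrolment in study V48P7E1". The Figure 2 legend gives them their own label, TBE_R_B: "R-schedule in V48P7 and Booster before enrollment in V48P7E1".

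Later visits are not timed from each subject's booster. The text before Table 6 says of Visit 23 that "it will need to be considered as the driver for the calculation of the interval for all subsequent visits".

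The analysis uses three groups, C, R and AC (SAP 10), assigned by parent-study schedule (Protocol 10.7.2, SAP 6.3.1). GMTs and schedule differences come "from an ANOVA model with group as fixed factor". The continuous baseline summaries in SAP 6.1.1 are limited to this: "age, height and weight at enrolment will be calculated overall and by vaccine schedule". Sex and ethnic origin are added, and SAP 6.1.2 adds a distribution by booster visit, which I read as the second booster given in this study.

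**The concern.** The two origins roughly coincide only for subjects boosted within V48P7E1. Anyone boosted earlier is, at every visit, further from the booster than the label states. Because all later visits are timed from Visit 23, a gap present there carries through to Visit 27. For these subjects the lower bound in the objective (11 years or more) still holds. The upper bound of 15 years and the starting point of year 1 in the waning description do not.

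Two things follow. The report would give the wrong follow-up time for most of one of three groups, by an amount it never shows. And R would be contrasted with C and AC at the same nominal year but at a different time since booster, so the difference and its 95% CI would mix primary schedule with elapsed time. Protocol 1.3 says the results may help prescribers time boosters for people on different primary schedules, so time since booster is the variable that matters most here.

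**Working it through.** **Planned numbers.** Table 1 gives C 51, R 46, AC 103; 51 + 46 + 103 = 200, which reproduces the stated total of approximately 200.

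**Share of R affected.** The Table 1 footnote gives 9 R subjects boosted in V48P7E1 and 40 before it, 49 in all.

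- Among boosted R: 40/49 = 81.6%.
- Among about 46 planned: at least 46 − 9 = 37 (80.4%), at most 40 (87.0%). If losses were random, 46 × 40/49 = 37.6.
- In C and AC: none.

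**Size of the offset.** Let d be the time from first booster to V48P7E1 enrolment. The documents establish only d > 0, so the values below are assumptions. They use the 12 to 18 months recommended after the rapid schedule (Protocol 1.2), the 3-year interval in the Figure 2 note, and last primary doses at Day 21 (R) and Day 300 (C, AC). With p the early-boosted share (37/46 to 40/46), the mean time in pooled R at nominal Year 15 is 15 + p × d.

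| Assumption | d (years) | Early-boosted R at nominal Year 1 / 11 / 15 | Pooled R mean at Year 15 |
|---|---|---|---|
| Small gap | 0.25 | 1.25 / 11.25 / 15.25 | 15.20–15.22 |
| Booster at 12–18 months; enrolment 3 years after own last primary dose | 3 − 1.5 = 1.5 to 3 − 1.0 = 2.0 | 2.5–3.0 / 12.5–13.0 / 16.5–17.0 | 16.21–16.74 |
| Same booster timing; enrolment 3 years after Day 300 | 3 + (300 − 21)/365.25 − 1.5 = 2.26, or − 1.0 = 2.76 | 3.26–3.76 / 13.26–13.76 / 17.26–17.76 | 16.82–17.40 |

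**Effect on the R:C contrast (illustration only).** Assume equal linear waning on the log10 scale and no true schedule effect. The simple form is GMT ratio = 10^−(slope × d × p), with an assumed slope of 0.02 to 0.08 log10 per year.

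A simulation (400,000 subjects per scenario) then added two rules from the plan: exclusion for NT below 10 in V48P7E2 (Protocol 4.3; applied at nominal Year 10) and NT = 1 at visits after the first value below 10 (Protocol 10.5 and 10.7.2). Its assumptions were slope 0.02, 0.05 or 0.08; SD 0.4 or 0.6; within-subject correlation 0.80 or 0.95; 90% or 97% at NT ≥10 at true 10 years; and 37 or 40 of 46 early-boosted. The last column is −log10 of the ratio with both rules.

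| d | Ratio, simple form | Ratio, both rules | NT ≥10 lower in R by (points) | Shift, log10 |
|---|---|---|---|---|
| 0.25 | 0.961–0.991 | 0.946–0.992 | 0.04–1.5 | 0.004–0.02 |
| 1.5 | 0.786–0.946 | 0.714–0.951 | 0.3–9.1 | 0.02–0.15 |
| 2.0 | 0.726–0.929 | 0.638–0.935 | 0.4–12.2 | 0.03–0.20 |
| 2.76 | 0.643–0.903 | 0.538–0.912 | 0.5–16.5 | 0.04–0.27 |

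**Against the precision of the study.** The simulated SD at Year 15 was 0.47 to 0.82. The R−C 95% half-width is 1.972 × SD × √(1/46 + 1/51), about 0.19 to 0.33 log10. The shift ranges from negligible against this width to comparable with it.

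**The case against.** The case for treating this as a small clarification has real weight.

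- **The offset is unknown.** Nothing says the 40 subjects were boosted at the recommended 12 to 18 months, and the largest offsets further assume that R was enrolled 3 years after Day 300. The lowest ratios also need the steepest assumed slope, and late flattening of waning would shrink them. This stands: the effect size cannot be stated. The labelling error needs only d > 0, which the documents give.
- **The comparisons are descriptive** (Protocol 10.9, SAP 7). No error rate or margin is affected, and at d = 1.5 the shift is below the half-width. This limits the consequence, but differences with 95% CIs will still be produced and the labels remain wrong.
- **The error is probably conservative for R.** If titres wane, extra elapsed time understates R persistence, and Protocol 1.2 reports above 90% at NT ≥10 for at least 10 years regardless of schedule. That stands for persistence; it does not make the R versus C and AC contrast fair.
- **An earlier first booster belongs to the registered rapid schedule**, so schedule and booster timing are partly inseparable. True, but time elapsed since that booster is a separate quantity and can be reported.
- **Early boosting is disclosed** (Protocol 3, 4.1 and 4.2), and Figures 2 and 3, not visible in the text reviewed, may show its timing. Disclosure does not re-anchor the analysis.
- **Protocol 10.1 summarises by the schedule received in V48P7E1**, which could be read as separating TBE_R_B. Protocol 10.7.2 and SAP 4.1 and 10 use the parent-study schedule and a single R group, so R is pooled.

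**Conclusion.** The concern holds. The visit labels and the objective use different origins, and they diverge for 37 to 40 of about 46 planned R subjects and for nobody in C or AC. The direction is certain: these subjects are later after their booster than labelled. The count rests only on the documents' figures and the approximate R size.

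The size of the offset, and so of any distortion in the R contrasts, is unknown. Under the stated assumptions it runs from negligible to a Year 15 R:C GMT ratio of 0.54, probably but not certainly to R's disadvantage. The finding does not depend on those illustrations. It is worth correcting because the plan, followed as written, would misreport time since booster for about four-fifths of one group. It does not invalidate the study.

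**What to change.** 1. State one time origin, and reconcile the notes to Tables 4 and 5 with Protocol 2.1 and 10.2 and SAP 3.1, 4.2 and 6.3.2.
2. Seek the pre-V48P7E1 booster dates through the subject-number link to the earlier studies (Protocol 5.2). Where they can be obtained, derive actual years since first booster and tabulate the median and range by group at each visit. Otherwise footnote these subjects as boosted before enrolment, time since booster unknown.
3. Label their persistence and waning results by actual time since booster where it is known, and show TBE_R_B beside pooled R. The remaining R stratum has only about 6 to 9 subjects and should be presented as very imprecise. The Clopper-Pearson lower limit is 66% with 9/9 and 54% with 6/6; at an assumed SD of 0.4 to 0.6, the GMT limits lie a factor of about 2.0 to 2.9 (n = 9) or 2.6 to 4.3 (n = 6) either side.
4. Optionally, use the repeated-measures model already allowed in SAP 6.3.2, pooled across visits with actual years since booster, as a sensitivity analysis. State that it depends on the assumed waning shape and the NT = 1 imputation and does not fully isolate schedule.

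The cost is a wording change, one derived variable and one summary table if the dates can be found, and one extra display. No new visits, samples or subjects are needed.

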# Will only be collected from subjects who received a second booster vaccination in this study, all SAEs will be collected for 1 month after vaccination.

Table 5 List of study procedures for ad hoc and additional visits

Timepoint(s)	Year 11		Year 12		Year 13		Year 14		Year 15	
Type of contact	Visit 23.1	Visit 23.2	Visit 24.1	Visit 24.2	Visit 25.1	Visit 25.2	Visit 26.1	Visit 26.2	Visit 27.1	Visit 27.2
	ad hoc visit 6 months after scheduled visit 23	21 days after ad hoc visit	ad hoc visit 6 months after scheduled visit 24	21 days after ad hoc visit	ad hoc visit 6 months after scheduled visit 25	21 days after ad hoc visit	ad hoc visit 6 months after scheduled visit 26	21 days after ad hoc visit	ad hoc visit 6 months after scheduled visit 27	21 days after ad hoc visit
Sampling timepoint(s)		post-vacc								
Check inclusion / exclusion criteria	•		•		•		•		•	
Medical history	•		•		•		•		•	
Physical examination	•		•		•		•		•	
Urine pregnancy test	•		•		•		•		•	
Check contraindications and warnings and precautions to vaccination	•		•		•		•		•	
Pre-vaccination body temperature	•		•		•		•		•	
Measure/record weight	•		•		•		•		•	
Vaccination										
Vaccine administration	•		•		•		•		•	
Date of vaccine administration	•		•		•		•		•	
30 minutes post booster injection assessment	•		•		•		•		•	
Laboratory Assays										
Blood sampling for antibody determination (~10 ml)		•		•		•		•		•
Safety assessments										
Record any concomitant medications/vaccinations	•		•		•		•		•	

